## Definition of SAE

An SAE is defined as any untoward medical occurrence that, at any dose:	
a) Results in death	
b) Is life-threatening	
The term ‘life-threatening’ in the definition of “serious” refers to an event in which the subject was at risk of death at the time of the event. It does not refer to an event, which hypothetically might have caused death, had it been more severe.

c) Requires inpatient hospitalisation or prolongation of existing hospitalisation	
In general, hospitalisation signifies that the subject has been detained (usually involving at least an overnight stay) at the hospital or emergency ward for observation and/or treatment that would not have been appropriate in the physician’s office or an outpatient setting. Complications that occur during hospitalisation are AEs. If a complication prolongs hospitalisation or fulfils any other serious criteria, the event will also be considered as serious. When in doubt as to whether “hospitalisation” occurred or was necessary, the AE should be considered serious.

d) Results in persistent disability/incapacity	
 
The term disability means a substantial disruption of a person’s ability to conduct normal life functions.
 
This definition is not intended to include experiences of relatively minor medical significance such as uncomplicated headache, nausea, vomiting, diarrhoea, influenza, and accidental trauma (e.g., sprained ankle) which may interfere with or prevent everyday life functions but do not constitute a substantial disruption.
 

e) Is a congenital anomaly/birth defect	
f) Other situations:	
 
Medical or scientific judgment should be exercised in deciding whether SAE reporting is appropriate in other situations such as important medical events that may not be immediately life-threatening or result in death or hospitalisation but may jeopardise the subject or may require medical or surgical intervention to prevent 1 of the other outcomes listed in the above definition. These events should usually be considered serious.
 
 
Examples of such events include invasive or malignant cancers, intensive treatment in an emergency room or at home for allergic bronchospasm, blood dyscrasias, or convulsions that do not result in hospitalisation.


If an event meets the criteria to be determined as “serious”, additional examinations/tests will be performed by the investigator in order to determine ALL possible contributing factors for each SAE.
 
Possible contributing factors include:
 
 
Medical history.
 
Other medication.
 
Protocol required procedure.
 
Other procedure not required by the protocol.
 
Lack of efficacy of the vaccine, if applicable.
 
Erroneous administration.
 
Other cause (specify).
 
 
Assessment of Outcome
 
The Investigator will assess the outcome of all unsolicited AEs (including SAEs) recorded during the study as:
 
 
Recovered/resolved.
 
	

- Recovering/resolving.
- Not recovered/not resolved.
- Recovered with sequelae/resolved with sequelae.
- Fatal (SAEs only).

## Recording and Follow-up of AE and/or SAE

### AE and SAE Recording

- When an AE/SAE occurs, it is the responsibility of the investigator to review all documentation (e.g., hospital progress notes, laboratory reports, and diagnostics reports) related to the event.
- The investigator will then record all relevant AE/SAE information in the eCRF. Each event must be recorded separately.
- It is **not** acceptable for the investigator to send photocopies of the subject's medical records to IQVIA in lieu of appropriate completion of the IQVIA/AE/SAE eCRF page.
- There may be instances when copies of medical records for certain cases are requested by IQVIA. In this case, all subject identifiers, with the exception of the subject number, will be redacted on the copies of the medical records before submission to IQVIA.
- The investigator will attempt to establish a diagnosis of the event based on signs, symptoms, and/or other clinical information. Whenever possible, the diagnosis (not the individual signs/symptoms) will be documented as the AE/SAE.

### Assessment of Intensity

The investigator will make an assessment of intensity for each AE and SAE reported during the study and assign it to one of the following categories:

- Mild: An event that is easily tolerated by the subject, causing minimal discomfort and not interfering with everyday activities.
- Moderate: An event that causes sufficient discomfort and interferes with normal everyday activities.
- Severe: An event that prevents normal everyday activities.

An AE that is assessed as severe should not be confused with an SAE. Severe is a category utilised for rating the intensity of an event; and both AEs and SAEs can be assessed as severe.

An event is defined as 'serious' when it meets at least one of the predefined outcomes as described in the definition of an SAE, NOT when it is rated as severe.

Assessment of Causality

The Investigator is obligated to assess the relationship between study vaccine(s) and the occurrence of each AE/SAE using clinical judgment. In case of concomitant administration of multiple vaccines, if possible, the Investigator should specify if the AE could be causally related to a specific vaccine administered (i.e., investigational or co-administered vaccine). When causal relationship to a specific vaccine(s) cannot be determined, the Investigator should indicate the AE to be related to all products.
 
Alternative plausible causes, such as natural history of the underlying diseases, concomitant therapy, other risk factors, and the temporal relationship of the event to the study vaccine(s) will be considered and investigated. The Investigator will also consult the SmPC and/or Prescribing Information (PI) for marketed products to determine his/her assessment.
 
There may be situations when an SAE has occurred and the Investigator has minimal information to include in the initial report to IQVIA. However, it is very important that the Investigator always makes an assessment of causality for every event prior to submission of the Expedited Adverse Events Report to IQVIA. The Investigator may change his/her opinion of causality in light of follow-up information and update the SAE information accordingly. The causality assessment is one of the criteria used when determining regulatory reporting requirements.
 
Causality of all unsolicited AEs should be assessed by the Investigator using the following question:
 
Is there a reasonable possibility that the AE may have been caused by the study vaccine?
 
YES: There is a reasonable possibility that the study vaccine(s) contributed to the AE.
 
NO: There is no reasonable possibility that the AE is causally related to the administration of the study vaccine(s). There are other, more likely causes and administration of the study vaccine(s) is not suspected to have contributed to the AE.
 

• Alternative causes, such as underlying disease(s), concomitant therapy, and other risk factors, as well as the temporal relationship of the event to study treatment administration will be considered and investigated.

• The investigator will also consult the SmPC and/or Product Information, for marketed products, in his/her assessment.

• For each AE/SAE, the investigator must document in the medical notes that he/she has reviewed the AE/SAE and has provided an assessment of causality.

• There may be situations in which an SAE has occurred, and the investigator has minimal information to include in the initial report to IQVIA. However, it is very important that the investigator always make an assessment of causality for every event before the initial transmission of the SAE data to IQVIA.

• The investigator may change his/her opinion of causality in light of follow-up information and send an SAE follow-up report with the updated causality assessment.

 
The causality assessment is one of the criteria used when determining regulatory reporting requirements.


Follow-up of AEs and SAEs

The investigator will provide any new or updated relevant information on previously reported SAE to GSK using a paper/electronic Expedited Adverse Events Report as applicable. The investigator is obliged to perform or arrange for the conduct of supplemental clinical examinations/tests and/or evaluations to elucidate the nature and/or causality of the AE or SAE as fully as possible.

## Reporting of SAEs

### SAE Reporting to IQVIA via an Electronic Data Collection Tool

- The primary mechanism for reporting an SAE to IQVIA will be the electronic data collection tool.
- If the electronic system is unavailable for more than 24 hours, then the study centre will use the paper SAE data collection tool (see next section).
- The study centre will enter the SAE data into the electronic system as soon as it becomes available.
- After the study is completed at a given study centre, the electronic data collection tool will be taken off-line to prevent the entry of new data or changes to existing data.
- If a study centre receives a report of a new SAE from a subject or receives updated data on a previously reported SAE after the electronic data collection tool has been taken off-line, then the study centre can report this information on a paper SAE form (see next section) or to the medical monitor/SAE coordinator by telephone.
- Contacts for SAE reporting can be found in the study reference manual.

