## 8.3 Adverse Events

### 8.3.1 Time Period and Frequency for Collecting AE and SAE Information

All SAEs will be collected from Visit 1 through study end, at the time points specified in the SoA [[Table 3](#)].

All AEs will be collected from vaccination through the 31-day follow-up period after each vaccination, as specified in the SoA [[Table 3](#)].

Medical occurrences that begin before the start of study treatment but after obtaining informed consent will be recorded on the Medical History/Current Medical Conditions section of the eCRF, not the AE section.

All SAEs will be recorded and reported to the Sponsor or designee within 24 hours, as indicated in [Appendix 4](#). The investigator will submit any updated SAE data to the Sponsor within 24 hours of it being available.

Investigators are not obligated to actively seek AEs or SAEs after conclusion of the study participation. However, if the investigator learns of any SAE, including a death, at any time after a subject has been discharged from the study, and he/she considers the event to be reasonably related to the study treatment or study participation, the investigator must promptly notify the Sponsor.

The method of recording, evaluating, and assessing the causality of AEs and SAEs and the procedures for completing and transmitting SAE reports are provided in [Appendix 4](#).

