### Back-up SAE Reporting to IQVIA via Paper (in Case of Electronic System Failure)

- Facsimile transmission of the SAE paper eCRF is the preferred method to transmit this information to the medical monitor or the SAE coordinator.
- In rare circumstances and in the absence of facsimile equipment, notification by telephone is acceptable with a copy of the SAE data collection tool sent by overnight mail or courier service.
- Initial notification via telephone does not replace the need for the investigator to complete and sign the SAE eCRF pages within the designated reporting time frames.
- Contacts for SAE reporting can be found in the study reference manual.

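### Protocol Appendix 4 sends sites to paper only after more than 24 hours of system outage, so a site that waits for that trigger can miss the 24-hour limit for an initial SAE report

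*Protocol*

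**What the plan says.** Protocol Section 8.3.1 sets the duty: "All SAEs will be recorded and reported to the Sponsor or designee within 24 hours". It points to Appendix 4 for how this is done and makes no exception for system failure. For follow-up data it adds: "The investigator will submit any updated SAE data to the Sponsor within 24 hours of it being available".

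Appendix 4, under *SAE Reporting to IQVIA via an Electronic Data Collection Tool*, names the normal route: "The primary mechanism for reporting an SAE to IQVIA will be the electronic data collection tool". The rule for an outage during the study follows: "If the electronic system is unavailable for more than 24 hours, then the study centre will use the paper SAE data collection tool". The same list has the site enter the data electronically once that is possible. Its only other paper provision covers the time after the tool is taken off-line at the end of the study at a centre.

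The next block, *Back-up SAE Reporting to IQVIA via Paper*, describes the means. Fax is preferred. The telephone is a narrow fallback: "In rare circumstances and in the absence of facsimile equipment, notification by telephone is acceptable". A call "does not replace the need for the investigator to complete and sign the SAE eCRF pages within the designated reporting time frames".

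Updates to an SAE already reported are also covered under *Follow-up of AEs and SAEs* in Appendix 4. That text accepts a paper or an electronic expedited report and attaches no outage condition.

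**The concern.** A back-up should open early enough to keep the deadline. Here the stated waiting time (more than 24 hours) exceeds the time allowed (24 hours). The cross-reference from Section 8.3.1 does not settle the matter, because Appendix 4 neither repeats the 24-hour limit nor says when the clock starts for an initial report.

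What is at stake is the timeliness of initial SAE reports in infants enrolled at 6 to 12 weeks of age, at about 35 centres. Section 8.3.4 treats prompt notification as essential to the sponsor's legal and ethical duties, and the sponsor's onward reporting to authorities depends on it. With that many centres, the written rule should not rely on each site finding its own way round a conflict.

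**Working it through.** The protocol states no figure to reproduce; the check is timing arithmetic.

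**Inputs**
- Limit for the initial report: 24 h (Section 8.3.1).
- Trigger for paper: system unavailable for more than 24 h (Appendix 4).
- Assumption: the 24 h run from site awareness. The documents give no starting point for initial reports.

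**Set-up.** Let the outage start at hour 0 and last d hours. The site becomes aware at hour a (negative means before the outage) and has not yet entered the SAE when the system fails. Then:
- deadline = a + 24;
- if d is 24 or less, the electronic system returns at hour d and paper is never triggered;
- if d exceeds 24, paper opens just after hour 24.

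A site that waits for the trigger is late if the first route to open comes after a + 24.

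| Case | a | d | Deadline | First route open | Result |
|---|---|---|---|---|---|
| A | 0 | 20 | 24 | electronic, 20 | on time, 24 − 20 = 4 h to spare |
| B | 0 | over 24 | 24 | paper, after 24 | late |
| C | −6 | over 24 | 18 | paper, after 24 | late by more than 24 − 18 = 6 h |
| D | −10 | 20 | 14 | electronic, 20 | late by 20 − 14 = 6 h, paper never triggered |
| E | +6 | over 24, counted from true start | 30 | paper, after 24 | can be on time, about 30 − 24 = 6 h left |
| F | +6 | over 30, counted from the site's first failed attempt at hour 6 | 30 | paper, after 6 + 24 = 30 | late |

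**Reading the table.** When the outage begins at or after awareness (a ≤ 0), the report is late exactly when the outage is still running at the deadline, that is, when d > a + 24 (cases B, C and D). Case A shows that an outage ending before the deadline causes no delay. Cases E and F differ only in where the 24 hours of unavailability are counted from, which the documents do not say.

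**Outer limit.** For the outage to matter it must start before the deadline, so a > −24. The time from awareness to the first open route is min(d, 24) − a, which approaches 24 + 24 = 48 h. That needs a site that has left the SAE unreported for almost the whole 24 hours, followed at once by an outage of about 24 hours or longer. It is a bound, not an expected delay.

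**The case against.** The strongest reply is that Appendix 4 makes paper compulsory after 24 hours of downtime but does not forbid it sooner. The 24-hour limit in Section 8.3.1 is unconditional, the back-up block is headed for system failure without a time threshold, and it keeps the duty to complete the SAE pages in time. A careful site could satisfy every passage by faxing the paper form before the deadline. This stands as far as it goes: the protocol does not force a late report. But the only trigger stated for an initial report during the study is the one above 24 hours. A site that takes it as its instruction can be late, and no passage gives an earlier one.

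Three stronger readings are tempting, and the documents do not support them:
- *Every report is late if the outage starts at awareness.* Not so; an outage that ends before hour 24 leaves time for electronic entry (case A).
- *SAE updates have the same defect.* The follow-up text in Appendix 4 already accepts paper or electronic reports without waiting for an outage of any length.
- *Safety oversight or the SAE results are compromised.* The trial has no data monitoring committee, but that does not change how SAEs are reported. Late SAEs are still recorded and still counted in the SAE endpoint.

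**Conclusion.** The point holds for initial SAE reports. Section 8.3.1 and the Appendix 4 trigger conflict as written, and a site that follows the trigger can exceed the 24-hour limit when an outage that began at or after awareness is still running at the deadline. The worked example gives a delay of 6 hours.

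The conclusion assumes that the clock starts at site awareness and that the site waits for the stated trigger. If awareness falls during an outage, the result depends on whether downtime is counted from its true start. Severity is minor to moderate: the consequence is a delay in safety reporting, outage frequency is not stated, and sample size, power, type I error, endpoints and analyses are untouched.

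**What to change.** Reconcile Section 8.3.1 with the two SAE reporting blocks of Appendix 4. Replace the outage trigger with a rule tied to the deadline, for example: if the electronic system is unavailable and the initial SAE report could not otherwise be made within the 24-hour limit, the study centre sends the paper SAE form in time to meet that limit and enters the data electronically once the system is restored. State in the same place when the 24 hours begin. For updates, only a cross-reference to the follow-up text in Appendix 4 is needed.

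The cost is a sentence or two in Appendix 4 and a matching line in the site instructions. The downside is occasional duplicate paper and electronic entry to reconcile, which Appendix 4 already foresees by asking for later electronic entry.

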### Back-up SAE Reporting to IQVIA via Paper (in Case of Electronic System Failure)

- Facsimile transmission of the SAE paper eCRF is the preferred method to transmit this information to the medical monitor or the SAE coordinator.
- In rare circumstances and in the absence of facsimile equipment, notification by telephone is acceptable with a copy of the SAE data collection tool sent by overnight mail or courier service.
- Initial notification via telephone does not replace the need for the investigator to complete and sign the SAE eCRF pages within the designated reporting time frames.
- Contacts for SAE reporting can be found in the study reference manual.

## Appendix 5      Protocol Amendment History

The Protocol Amendment Summary of Changes Table for the current amendment is located directly before the Table of Contents (TOC).

### **Protocol Amendment 1** (additions **bold** and *italic*; deletions strikethrough ~~and~~):

Synopsis and Section 3.0: Addition of “ $\geq$ ” to the secondary immunogenicity objective, preceding the numbers of the thresholds for short-term and long-term protection:

To assess the immunogenicity of Hib-components in terms of percentage of subjects above the thresholds for short-term ( $\geq 0.15 \mu\text{g/mL}$ ) and long-term ( $\geq 1.0 \mu\text{g/mL}$ ) protection as well as in terms of GMCs (post primary, pre- and post-booster vaccination).

#### Section 6.6:

Exclusionary concomitant therapies are described in exclusion criteria Section 5.2.2.

*At each trial visit/contact, the investigator or delegate should question the participant's parent(s)/LAR(s) about any medications/products taken and vaccinations received by the participant. The following concomitant medications/products/vaccines must be recorded in the eCRF:*

- *All concomitant medications/products associated with an AE, except vitamins and dietary supplements, administered following each dose of investigational vaccine (Day 1 to Day 31).*
- *Any vaccination administered in the period from birth until 30 days after the last dose of study vaccines.*
- *Prophylactic medication (i.e., medication administered in the absence of ANY symptom and in anticipation of a reaction to the vaccination or blood sampling), for example:*
  - *An antipyretic is considered to be prophylactic when it is given in the absence of fever and any other symptom to prevent fever from occurring (fever is defined as temperature  $\geq 38.0^\circ\text{C}$  [ $100.4^\circ\text{F}$ ] regardless of the location of measurement).*
  - *A topical local anesthetic used prior to a blood sampling is considered to be prophylactic.*
- *Any concomitant medications/products/vaccines listed in Section 5.2.2.*
- *Any concomitant medications/products/vaccines relevant to an SAE or administered at any time during the trial period for the treatment of an SAE. In addition,*

***concomitant medications relevant to SAEs need to be recorded on the Expedited AE Report.***

~~These concomitant medications/vaccinations information will be collected at each study visit. medications/products/or vaccines (including over the counter or prescription medicines) that the subject is receiving at the time of enrolment (or within 14 to 30 days before the time of enrolment, as detailed in Section 5.2.2) or receives during the study must be recorded on the eCRF along with:~~

- Reason for use.
- Dates of administration including start and end dates.
- Dosage information including dose and frequency.

The Medical Monitor should be contacted if there are any questions regarding concomitant or prior therapy.

~~A list of excluded medications/therapy is provided in Section 5.2.2.~~

Prophylactic administration of antipyretics (paracetamol/acetaminophen and ibuprofen) before or immediately after vaccine administration can reduce the incidence and intensity of post-vaccination febrile reactions.

Abbreviation	Definition
MedDRA	Medical Dictionary for Regulatory Activities
mL	Millilitre
NI	Non-inferiority
PD	Protocol deviation
PDMP	Protocol deviation management plan
PRI	Primary
PRP	Polyribosylribitol phosphate
PT	Preferred term
PPS	Per Protocol Set
SAE	Serious adverse event
SAP	Statistical analysis plan
SD	Standard deviation
SOC	System organ class
UL	Upper limit
ULOQ	Upper limit of quantification
V	Visit

Document : \quintiles.net\enterprise\Apps\sasdata\SASb\SAS\GSK\Infanrix\PPD \Biostatistics\Documentation
n\SAP

Author: PPD Version Number: 1.0

Version Date: [07JAN2021]

Template No.: CS_TP_BS016 Revision 6

Reference: CS_WI_BS005

Effective Date: 02Dec2019

1. INTRODUCTION

This document describes the rules and conventions to be used in the presentation and analysis of safety and immunogenicity data at final analyses for Protocol 212645. It describes the data to be summarised and analysed, including specifics of the statistical analyses to be performed. This statistical analysis plan (SAP) is based on the original Protocol Version 1 dated 21 Feb 2020.

2. STUDY OBJECTIVES

2.1. PRIMARY OBJECTIVE

The co-primary objectives are:

- To demonstrate that the Hib response in Investigational group (Inv_group) is non-inferior to the Comparator group (Com_group), 1-month post-booster vaccination in terms of:
 - Geometric Mean Concentration (GMCs)
 - Criterion: Lower limit (LL) of the 2-sided 95% confidence interval (CI) on group GMC ratio (Inv_group over Com_group) is above 0.5.
 - Percentage of subjects with anti-PRP antibody concentrations $\geq 5 \mu\text{g/mL}$.
 - Criterion: First primary objective is met and the LL of the 2-sided 95% CI on group difference in the percentage (Inv_group minus Com_group) is above -10%.
- To demonstrate that the Hib response in Inv_group is superior to Com_group, 1-month post-booster vaccination in terms of:
 - GMCs
 - Criterion: All previous objectives are met and the LL of the 2-sided 95% CI on group GMC ratio (Inv_group over Com_group) is above 1.
 - Percentage of subjects with anti-PRP antibody concentrations $\geq 5 \mu\text{g/mL}$.
 - Criterion: All previous objectives are met and the LL of the 2-sided 95% CI on group difference in the percentage (Inv_group minus Com_group) is above 0.
- Note: A hierarchical procedure will be used to control the risk of concluding erroneously.

Document : \quintiles.net\enterprise\Apps\sasdata\SASb\SAS\GSK\Infanrix\PPD \Biostatistics\Documentation\NSAP

Author: PPD Version Number: 1.0

Version Date: [07JAN2021]

Template No.: CS_TP_BS016 Revision 6

Reference: CS_WI_BS005

Effective Date: 02Dec2019

